5.4.3 Missing or Partial Dates of Adverse Events or Concomitant Medications

Adverse events with incomplete start or stop dates (i.e., either day or month is missing) will be considered treatment-emergent adverse events (TEAE) unless the partial start date or the stop date confirms the AE started or ended prior to Study Day 1 (e.g., the day of the AE start date is unknown but the month and year indicate that the AE starts prior to Study Day 1). Adverse events with missing relationship to study drug will be included in the “Related” category for the summary tables and footnoted. Adverse events with missing severity will not be included in the by-severity summary table but will be footnoted in the table.

When there is incomplete information regarding dosing dates for prior and concomitant medication, the medication will be considered as a concomitant medication unless it contradicts with the stop date. For example, a medication will be considered a prior medication if the month and year of the end date indicates a date before Study Day 1 even though the start date could be missing.

5.5 Interim Analysis

No interim analysis is planned.

5.6 Timing of Data Analyses

There will be 2 database locks for this study:

- A provisional database lock after all subjects complete the Day 169 visit to allow for the analysis of safety and efficacy data through Day 169.
- A final database lock after all subjects complete the study to allow for the analysis of any safety data collected after Day 169.

For each database lock, applicable EDC data will be locked in order to protect write access after the following preconditions are fulfilled:

- All records are entered in the database.
- All AE are coded to the satisfaction of the Chief Medical Officer.
- All medications are coded to the satisfaction of the Chief Medical Officer.
- All data queries have been resolved.
- All decisions have been made regarding all protocol violations and ITT population exclusions.
- Written authorizations to lock the database are obtained from Allakos Clinical Data Management and the Chief Medical Officer.

The randomization code for this study will not be revealed until the previous preconditions are fulfilled and documentation of the provisional database lock is complete. After the provisional database lock, the randomization code will be made available to a restricted number of individuals at Allakos who are involved in the data analysis. Data analysis will commence after the provisional data lock and the final database lock, respectively. In addition, the PK and ADA data may be locked and assessed separately.

5.7 Multicenter Study

Analysis will be performed pooling data across study sites.

The study will have approximately 60 sites. Analysis of site effect will be based on analysis centers. Analysis centers will be formed in such a way that there are sufficient subjects per pooled analysis center for the assessment of site effects. Sites from the following geographic clusters have been identified for pooling data across study sites:

- **Analysis Center 1:** Massachusetts, Connecticut, Rhode Island, New York, New Jersey, Pennsylvania, District of Columbia, Maryland, Maine, Vermont, Delaware, and New Hampshire
- **Analysis Center 2:** Virginia, West Virginia, South Carolina, Georgia, Mississippi, Florida, Alabama, Louisiana
- **Analysis Center 3:** North Carolina, Tennessee, Ohio, Michigan, Indiana, Kentucky
- **Analysis Center 4:** South Dakota, Arkansas, Minnesota, Wisconsin, North Dakota, Illinois, Missouri, Iowa, Texas, Oklahoma, Kansas, Nebraska, Wyoming, Colorado
- **Analysis Center 5:** Utah, New Mexico, Arizona, California, Oregon, Washington, Idaho, Hawaii, Alaska, Montana, Nevada

5.8 Multiple Comparisons/Multiplicity Adjustment

To control for the family-wise type-I error rate, the following testing procedures will be implemented:

Test each co-primary efficacy endpoint at 2-sided $\alpha=0.05$ level.

- If $p\leq 0.05$ for both co-primary endpoints, then reject the null hypothesis that AK002 is no different from placebo and accept the alternative hypothesis that AK002 is superior to placebo in reducing tissue eosinophil count and TSS score.
- If $p\leq 0.05$ for both co-primary endpoints, the hypothesis tests for the secondary endpoints will proceed in the prespecified order.
- If $p>0.05$ for either co-primary endpoint, the null hypothesis is accepted. No hypothesis test will be performed for the secondary endpoints.
- The issue of multiplicity of secondary endpoints will be handled by statistical testing of these outcomes in a hierarchical fashion. The order of secondary endpoints is described in Section 2.2. If at any point during the analysis of the secondary endpoints, the statistical test is not significant at 2-sided $\alpha=0.05$ level, the hypothesis testing procedure will stop. AK002 will be deemed superior to placebo for all endpoints prior to the stop.

5.9 Examination of Subgroups

Key endpoints will be summarized by subgroup to assess the consistency of the treatment effect across subgroups. Subgroups to be considered are:

- Baseline TSS ($<28, \geq 28$)
- Disease strata (EG \pm EoD, EoD)
- Gender (Male, Female)
- Age ($<65, \geq 65$)
- Race (White, Non-White)

6. Statistical Analysis

6.1 Analysis Populations

The population of “all screened subjects” comprises subjects who signed the informed consent (ICF).

6.1.1 Safety Population

The safety population comprises randomized subjects who have received at least 1 dose of the study drug.

6.1.2 Intent-to-Treat Population

The intent-to-treat (ITT) population is defined as subjects who were randomized to treatment.

6.1.3 Modified Intent-to-Treat Population

The modified intent-to-treat (MITT) population is defined as subjects who were randomized and received at least 1 dose of the study drug.

6.1.4 Per Protocol Analysis Population

The per protocol (PP) population will include the MITT population who have received at least 1 dose of study drug and did not have major protocol violations potentially interfering with the efficacy assessment. The PP exclusion criteria will be specified prior to the database lock and unblinding.

6.1.5 Primary Analysis Population

The MITT population is the primary analysis population for all efficacy and safety analyses. Analysis using the ITT population will be carried out if ≥ 5 randomized subjects do not receive study drug. The PP population will be used to evaluate robustness for the primary endpoints and select secondary endpoints when appropriate.

6.2 Disposition of Subjects

Subject demographics and reasons for screening failure will be summarized for screen-failed subjects. Subjects (n and %) who completed or discontinued from the study will be tabulated by treatment group and for both treatment groups combined. The primary reasons for study discontinuation will be included in the tabulation. The primary reasons may include, but are not limited to, any of the following:

- Subject withdrew consent
- Lost to follow-up
- Administrative reason
- Adverse event
- Investigator decision
- Failure to follow required study procedures
- Other

Subject disposition will be summarized for all enrolled subjects. Subject counts for the Safety, MITT, and PP populations will be included in the table. A data listing for subject disposition will be presented for all enrolled subjects.

6.3 Protocol Deviations

Protocol deviations will include, but are not limited to

- Non-compliance with scheduled study visit
- Non-compliance with study treatment
- Received prohibited medications (see Protocol Section 8.1)
- Non-compliance with study inclusion or exclusion criteria
- Non-compliance with study assessment procedures

Subjects with major protocol deviations will be listed. The listing will include a brief description of the deviation, deviation category, and if applicable, study day when deviation occurred along with other pertinent information. If warranted by the sample size, subjects (n and %) with major protocol deviations will be tabulated by treatment group and by deviation category.

Subjects who are excluded from the PP population will be listed with reasons for exclusion.

6.4 Demographics and Baseline Subject Characteristics

Descriptive statistics for subject characteristics and baseline values will be presented for all populations by treatment group and both treatment groups combined. Continuous variables will be summarized with n, mean, SD, and median. Categorical variables will be summarized with n and % of subjects for each category for the MITT and PP populations.

6.5 Baseline Disease Characteristics

Baseline disease characteristics including demographics, weight, blood eosinophils (≥ 500 cells/ μ L), IgE, history of atopic dermatitis, functional GI symptoms, history of EG and/or EoD, gastric eosinophils (per 5 hpf in subject with EG), duodenal eosinophils (per 3hpf in EoD), TSS total score at baseline, TSS (<28 vs. ≥ 28), PRO symptom scores, and baseline elevated esophagitis histologic criteria will be included in the subject data listing.

6.6 Medical History

Subject incidence (n and %) of medical history (and current medical condition before signing the informed consent) will be tabulated by the Medical Dictionary for Regulatory Activities (MedDRA), version 21.0) System Organ Class (SOC) and Preferred Term (PT).

6.7 *Electrocardiogram*

A listing of electrocardiograms (ECG) overall interpretation at screening visit will be provided.

6.8 *Pregnancy Test*

A listing of pregnancy test results will be provided.

6.9 *Baseline Diet*

A listing of baseline and on-study diet assessment and compliance will be provided.

6.10 *Treatments*

6.10.1 *Treatment Compliance and Extent of Exposure*

Summaries of treatment compliance and exposure to AK002 will be based on the safety population.

Duration of treatment exposure is defined as the total number of days a subject is exposed to the study treatment. This will be calculated for each subject by taking the difference between the date of last dose minus the date of first dose, plus 1 (date of last dose – date of first dose +1). Duration of exposure will be summarized using descriptive statistics (n, mean, standard deviation, median, minimum, and maximum).

Treatment compliance is defined as the number of infusions that subjects received divided by 6 (i.e., total number of infusions expected) $\times 100\%$. Treatment compliance will be summarized descriptively. In addition, an overall compliance that includes adherence to treatment administration schedule and any interruptions will be included in the data listing.

The treatment infusion information (length, volume, rate, and interruption) will be included in the subject data listing.

6.10.2 *Prior, Concomitant, and Newly Initiated Medications*

Prior medications and concomitant medications will be extracted from the Prior/Concomitant Medication CRF. Medications taken prior to Study Day 1 will be considered as prior medications; medications taken on or after Study Day 1 will be considered as concomitant medications; and newly initiated medication refers to any medication with a start date \geq Study Day 1. We note that a Prior Medication may also be a Concomitant Medication if the start date is prior to Study Day 1 and the end date is on/after Study Day 1. Medications will be coded using the WHO Drug Dictionary (WHODD March 2018 release) for PT and Anatomical Therapeutic Chemical (ATC) classification.

Medications will be tabulated separately based on the Safety population. The number (n and %) of subjects taking at least 1 medication and the number (%) of subjects taking each medication at the preferred term level will be tabulated by ATC4, and PT. Subjects taking the same PT medication twice will only be counted once.

A subject data listing will be provided to include the reported medication name, the WHODD PT, ATC4, study day and pertinent subject information. A separate data listing will include subjects who have received prohibited medications.

6.11 Analysis of Primary Efficacy Endpoints

To assist the data interpretation, all ICE will be listed with pertinent subject information (subject ID, date of last infusion, ICE start/stop day, nature of ICE (reason for treatment/study discontinuation if applicable, description of AE, description of prohibited/restricted medication), baseline tissue eosinophil count and TSS, and most recent tissue eosinophil count and 2-week average of TSS). A summary table will be created to present number of subjects (n, %) by treatment group:

- Subjects with any ICE
 - Subjects by ICE category

6.11.1 Analysis of the First Co-Primary Endpoint

The first co-primary endpoint will be analyzed using the imputed data set (Section 5.4.1). Fisher's exact test (primary analysis) will be conducted comparing AK002 with placebo for the proportion of tissue eosinophil responders. Proportion of responders and the associated 95% confidence interval will be presented for each treatment group. The between group difference and the associated 95% confidence interval will also be computed and presented. A sample SAS code is as follows.

```
* COMPUTE 95% EXACT CONFIDENCE INTERVAL FOR %RESPONSE FOR INDIVIDUAL
TREATMENT ;
ods output BinomialCLs=CL ;
proc freq data=ADEF ;
  table RESP / out=CNTS bin(cl=midp) ;
  by TRTAN ;
run;

* COMPUTE 95% EXACT CONFIDENCE INTERVAL AND FISHERS EXACT P-VALUE FOR
BETWEEN TREATMENT DIFFERENCE ;
ods output FishersExact=PVAL(where=(name1='XP2_FISH'))
RiskDiffCol2=DIFF(where=(row='Difference')) ;
proc freq data=ADEF ;
  table TRTPN*RESP / riskdiff(cl=exact) exact ;
run ;
```

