3.2.3 Methods of Assigning Subjects to Treatment Group

Approximately 160 subjects with symptomatic EG and/or EoD will be stratified by baseline TSS and disease status (EG \pm EoD, EoD). Subject will be randomized 1:1 to receive 1 of 2 dose regimens using stratified randomized blocks in a double-blind manner.

- AK002 at 1 mg/kg for the first dose followed by 3 mg/kg administered every 4 weeks for 5 subsequent doses.
- 6 doses of placebo

It is anticipated that at least 90 subjects with EG \pm EoD will be enrolled, and up to 70 subjects with EoD without EG will be enrolled.

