3.5 Determination of Sample Size

A total of approximately 160 subjects will be enrolled.

First Co-Primary Endpoint: A sample size of 80 subjects per treatment group will have >99% power to demonstrate a greater proportion of tissue responders at Week 24 in AK002 subjects when compared to placebo subjects, assuming the proportions of responders are 0.6 and 0.1 in AK002 and placebo groups, respectively.

Second Co-Primary Endpoint: A sample size of 80 subjects per group will provide 96% power to detect a statistically significant difference of 7.4 points between AK002 and placebo in the mean reduction from baseline in TSS at Weeks 23–24, assuming a common standard deviation of 12.5 points and a population mean baseline TSS of 30 points.

4. Definitions

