6.11.2 Sensitivity Analysis of the First Co-Primary Endpoint

Sensitivity analysis may be carried out using the Cochran-Mantel-Haenszel (CMH) test stratified by the randomization stratification factors (baseline TSS [<28 vs. ≥ 28] and Disease Strata [EG \pm EoD vs. EoD]) to assess robustness of the Fisher's exact test results.

A sample SAS code for the pairwise comparison is as follows.

```
* COMPUTES CMH P-VALUE AND NEWCOMBE COMMON RISK DIFFERENCE ;
ods output CMH=PVAL(where=(alhypothesis='Row Mean Scores Differ'));
CommonPdiff=DIFF;
proc freq data=ADEF ;
  tables TSS_STRAT*DISEASE_STRAT*TRTP*RESP / cmh commonriskdiff
  (cl=NEWCOMBE) ;
run ;
```

The rationale for specifying the Fisher's exact test as the primary analysis as opposed to specifying the CMH is because when a stratum has 100% response for 1 treatment group and 0% response for another treatment group, the CMH test may lose efficiency or not be computable. This is evident from the Phase 2 study outcome.

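### The SAP 6.11.1 sample code for the first co-primary mixes actual and planned arms, uses opposite response levels in its two steps, and labels mid-p and Wald intervals as exact

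*SAP*

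**What the plan says.** SAP 6.11.1 makes Fisher's exact test the primary analysis of tissue eosinophil response. It also calls for the responder proportion in each arm and the between-arm difference, each with a 95% confidence interval. SAP 4.2.6 makes that difference and its interval a summary measure of the estimand. Neither these sections nor Protocol 15.6.1 says how the intervals are computed, so the only detail is in the two PROC FREQ steps printed in 6.11.1:

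- The per-arm step, "table RESP / out=CNTS bin(cl=midp"), runs by `TRTAN`.
- The test and difference step is "table TRTPN*RESP / riskdiff(cl=exact) exact". It saves the two-sided Fisher p-value and the difference row of `RiskDiffCol2`.

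The comments above both steps describe the intervals as exact. The MITT population is "subjects who were randomized and received at least 1 dose of the study drug", which does not say whether arms are as randomized or as treated. The coding of `RESP` is not given anywhere. The sensitivity code in 6.11.2 uses `TRTP` and a Newcombe interval. On success, SAP 5.8 says: "Test each co-primary efficacy endpoint at 2-sided $\alpha=0.05$ level".

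**The concern.** A programmer who follows the code as printed would produce a display that differs from its description in three ways.

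1. **Treatment variable.** In ADaM, the standard SAP 5.1 adopts, TRTA variables hold actual treatment and TRTP variables planned treatment. If any patient received the wrong arm's treatment, the per-arm rates would not match the difference beside them.
2. **Response level.** The binomial option without LEVEL= reports the first sorted level of `RESP`. `RiskDiffCol2` is the second. Under any two-level coding the steps describe opposite outcomes.
3. **Interval type.** In the TABLES statement, the EXACT option requests Fisher's test. Exact limits for a risk difference also need RISKDIFF in an EXACT statement, and there is none. The saved row then holds asymptotic Wald limits under an exact label. The per-arm interval, also labelled exact, is mid-p.

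What is at stake is the reported estimate and interval for a co-primary endpoint, and for the endpoints in 6.12.2 and 6.12.3, which refer back to 6.11.1.

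**Working it through.** **Inputs.** From SAP 3.5: 80 per arm, "assuming the proportions of responders are 0.6 and 0.1 in AK002 and placebo groups, respectively". From SAP 3.2.3: 1:1 allocation. From SAP 5.8: two-sided 0.05. SAS behaviour is read from the syntax and was not executed.

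**The plan's own figure.** SAP 3.5 states "A sample size of 80 subjects per treatment group will have >99% power". With a pooled null variance, z = [0.5 − 1.96·√(2·0.35·0.65/80)] / √(0.6·0.4/80 + 0.1·0.9/80) = (0.5 − 0.1478)/0.0642 = 5.48, so power is 0.99999998. Exact enumeration for Fisher's test gives 0.9999999. The figure reproduces.

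**The two steps side by side.**

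| | Per-arm step | Test and difference step |
|---|---|---|
| Treatment | `TRTAN` (actual) | `TRTPN` (planned) |
| Level of `RESP` | first (no LEVEL=) | second (`RiskDiffCol2`) |
| Label in comment | exact | exact |
| Interval computed | mid-p | Wald |

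**Response level.** Take 48/80 and 8/80, the planning rates. Mid-p intervals for responders are 0.490 to 0.703 (AK002) and 0.048 to 0.181 (placebo). If `RESP` is coded 0/1 or N/Y, an assumption, the code returns the mirror image: 0.297 to 0.510 around 40%, and 0.819 to 0.952 around 90%. Fisher's p is 2.1e-11 with either level first, so the test does not depend on this.

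**Mid-p against exact, per arm.** Clopper-Pearson gives 0.484 to 0.708 and 0.044 to 0.188, slightly wider than mid-p.

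**Sign.** The code in 6.11.5 uses 0 for placebo. If that coding applies here (an assumption), row 1 minus row 2 is placebo minus AK002 and prints as −0.500.

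**Interval for the difference at 48/80 versus 8/80.**
- Wald: 0.5 ± 1.96·0.0642 = 0.374 to 0.626, width 0.252.
- Exact unconditional, score statistic: 0.362 to 0.621, width 0.259.
- Exact unconditional, unstandardized: 0.351 to 0.630, width 0.279.

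**Coverage, 80 per arm.** Sum Bin(x; 80, p1)·Bin(y; 80, p2) over all (x, y) whose interval contains p1 − p2.

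| p1 / p2 | Source | Wald | Newcombe |
|---|---|---|---|
| 0.60 / 0.10 | SAP 3.5 | 94.8% | 94.8% |
| 0.95 / 0.02 | assumed | 91.7% | 94.2% |
| 0.97 / 0.01 | assumed | 82.7% | 94.9% |

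At 100% versus 0% the Wald standard error is √(1·0/80 + 0·1/80) = 0, so the interval is the single point 1. For Newcombe, the Wilson lower limit for 80/80 is 1/(1 + 3.84/80) = 0.954 and the upper limit for 0/80 is 0.046. The lower limit for the difference is therefore 1 − √(0.046² + 0.046²) = 0.935.

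**Near the significance boundary.** At 18/80 versus 8/80, Fisher p = 0.052, but Wald is 0.125 ± 1.96·0.0575 = 0.012 to 0.238 and excludes zero. The exact score interval, 0.010 to 0.245, also excludes zero; the unstandardized one, −0.036 to 0.281, does not. Agreement with Fisher therefore depends on the method chosen, and replacing Wald does not guarantee it.

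**The case against.** The strongest reply is that this is sample code beneath correct prose. The prose asks for responder proportions and 95% intervals without calling them exact, and SAP section 7 requires independent reprogramming with matching results. A responder/non-responder swap is conspicuous and recoverable, since the OUT= data set keeps counts for both levels and mid-p limits mirror exactly. The reply is fair, but it does not settle the matter. The prose names neither an interval method nor a treatment variable, and two programmers working from the same code can reproduce the same error.

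Four stronger readings are tempting and are not supported:

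- **That the primary test is compromised.** A two-sided Fisher test has no response level, and it already runs on planned treatment.
- **That the per-arm display will show 40% and 90%.** This needs 0/1 or N/Y coding, which the SAP does not state. If responders sort first, the per-arm intervals are right and the saved difference is the one for non-response.
- **That Phase 2 shows Wald will fail here.** The remark about "when a stratum has 100% response for 1 treatment group and 0% response for another treatment group" concerns strata in the CMH test, whereas this interval is unstratified. The Phase 2 responder rates printed in Protocol 2.3 (70% and 68% versus 5%) are for a different, composite endpoint. Even at those rates, with 80 per arm, Wald covers 93.7% and 94.5%.
- **That the same interval applies in subgroups.** SAP 6.11.3 specifies only Fisher's test.

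**Conclusion.** The point holds as a specification error in the reporting of the first co-primary, not as a threat to its test. The treatment-variable mismatch is visible on the page and changes results only if someone received the wrong arm's treatment. The opposite response levels and the Wald limits follow from standard SAS behaviour, which should be confirmed by running the code. Which step shows non-responders depends on a coding the SAP does not give.

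The Fisher p-value and the 5.8 decision are unaffected by the level and interval problems. The numerical effect is small at the planning rates: Wald and exact limits differ by about 0.02 at most, and Wald coverage equals Newcombe's at 94.8%. Material under-coverage appears only at extreme rates that are assumptions. The correction is worth making before unblinding because the interval is a named summary measure and the code is its only definition.

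**What to change.** In SAP 6.11.1:

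1. Use `TRTPN` in both steps.
2. State the coding of `RESP` and add LEVEL= so that the per-arm step reports responders. Check that the saved risk-difference column is the same level.
3. Order the rows so that the difference is AK002 minus placebo.
4. For the difference, either add `exact riskdiff(method=score);` and save the table that holds the exact limits, or specify Newcombe (already used in 6.11.2) or Miettinen-Nurminen and drop the word exact.
5. Relabel the per-arm interval as mid-p, or change it to Clopper-Pearson.
6. State that Fisher's test governs if the test and the interval disagree.

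Carry the changes into 6.12.2 and 6.12.3, and into 6.11.3 if subgroup intervals will be shown. Run the revised code on dummy data to confirm which level and which limits are saved.

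The cost is a few lines of code and, with the exact score option, a slightly wider interval: 0.259 against 0.252 at the planning rates.
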